7. TREATMENT OF SUBJECTS

7.1. Dosing Schedule and Premedications

7.1.1. Plamotamab Dosing Schedule and Premedications

Subjects in Part 1 and those randomized to Arm A in Part 2 will be administered plamotamab IV [REDACTED] In Cycle 1, plamotamab will be administered once every 7 days (\pm 1 day) for 4 doses; beginning with Cycle 2, plamotamab will be administered every 2 weeks.

Subjects in Cohort 1A and Cohort 1B receive plamotamab according to the doses and schedule in [Table 12](#).

Table 12: Cohorts 1A and 1B Plamotamab Dosing Regimen

Cohort	Dose Level	Cycle 1 Day 1 (Priming Dose)	Cycle 1 Day 8	Cycle 1 Day 15	Cycle 1 Day 22	Cycle 2 Day 1	Cycle 2 Days 1, 8, 15, and 22	Cycle 3 and Subsequent Q2W Dosing
1A	-1	0.8 mg	2 mg	20 mg	20 mg	20 mg	20 mg	20 mg
1B	1	0.8 mg	2 mg	20 mg	35 mg	50 mg	50 mg	50 mg

Q2W = every 2 weeks.

The dose and schedule of plamotamab for Part 2 will be determined in Part 1.

Adjustments may be made to the infusion rate to increase the length of infusion time based on the Investigator's judgement of safety. Due to pump accuracy variations, infusions ending within 5 minutes prior to the required [REDACTED] period will not be considered a deviation.

Administer plamotamab at least 2 hours after tafasitamab on days when both products are given. All subjects in Part 1 and randomized to Arm A in Part 2 will be premedicated for plamotamab doses as indicated in [Table 13](#).

Table 13: Premedications for Plamotamab

	Cycle 1	Subsequent Cycles
Dexamethasone (if plamotamab alone is administered)	20 mg IV approximately 1 hour prior	Optional
Diphenhydramine	25 mg PO or IV approximately 30 to 60 minutes prior	Required
Acetaminophen	650 mg PO approximately 30 to 60 minutes prior	Required

IV = intravenous; PO = by mouth.

Subjects who have received 4 consecutive infusions at a stable dose and schedule without CRS or infusion reactions may have their premedications modified at the discretion of the Investigator.

In the event of the discontinuation of plamotamab, in the absence of disease progression, and if the subject is still receiving benefit from the study treatment, subjects may continue with other study treatment(s).

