- 2) Tafasitamab (tafasitamab-cxix) is a CD19-directed cytolytic antibody indicated for use in the US in combination with lenalidomide for the treatment of adult patients with R/R DLBCL not otherwise specified (NOS), including DLBCL arising from low-grade lymphoma, and who are not eligible for ASCT.
- 3) Lenalidomide, a thalidomide analogue, is an immunomodulatory agent (IMiD[®]) with antiangiogenic and antineoplastic properties. It is indicated for the treatment of adult patients with multiple myeloma, myelodysplastic syndromes, mantle cell lymphoma, follicular lymphoma, and marginal zone lymphoma.

Study Drug Dose Administration and Regimen:

Plamotamab (XmAb13676) – Subjects in Part 1 and those randomized to Arm A in Part 2 will be administered plamotamab IV [REDACTED]

In Cycle 1, plamotamab will be administered once every 7 days (\pm 1 day) for 4 doses; beginning with Cycle 2, plamotamab will be administered every 2 weeks (Q2W). Doses of plamotamab anticipated for use during the study via IV infusions include: 0.8 mg, 2 mg, and 20 mg. Refer to dosing table below.

Tafasitamab and plamotamab must not be administered simultaneously. On days when both tafasitamab and plamotamab are given, the tafasitamab should be given first followed by plamotamab. It is recommended that the infusions are separated by at least 2 hours.

Part 1, Cohort 1A and 1B, Plamotamab Dosing Regimen

Cohort	Dose Level	Cycle 1 Day 1 (Priming Dose)	Cycle 1 Day 8	Cycle 1 Day 15	Cycle 1 Day 22	Cycle 2 Day 1	Cycle 2 Days 1, 8, 15, and 22	Cycle 3 and Subsequent Q2W Dosing
1A	-1	0.8 mg	2 mg	20 mg	20 mg	20 mg	20 mg	20 mg
1B	1	0.8 mg	2 mg	20 mg	35 mg	50 mg	50 mg	50 mg

Q2W= every 2 weeks.

Tafasitamab: All subjects will receive tafasitamab. Priming doses will be administered on Days -8 and -4 of a 1-week run-in period. During the first 3 cycles of the study, tafasitamab will be infused on Day 1, Day 8, Day 15, and Day 22 of each cycle. Thereafter, tafasitamab will be administered on a biweekly (every 14 days) basis, with infusions on Days 1 and 15 of each 28-day cycle until disease progression, unacceptable toxicity, or discontinuation for any other reason, whichever comes first. Refer to dosing table below. Tafasitamab and plamotamab must not be administered simultaneously. On days when both tafasitamab and plamotamab are given, the tafasitamab should be given first followed by plamotamab. It is recommended that the infusions are separated by at least 2 hours.

Tafasitamab Dosing Regimen

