2.4.2. Non-Hodgkin's Lymphoma: Flat-Dosing Cohorts

In the flat-dosing cohort (Cohort 1N-C, weekly titration of 0.8, 2, 20, 35 and 50 mg, followed by weekly dosing of 50 mg until Cycle 3 then every-two-week dosing of 50 mg) of NHL subjects, data are available for 14 subjects as of 18 August 2021. Of those subjects, the most frequent AEs (> 20%) were cytokine release syndrome (8/14, 57.1%), nausea (7/14, 50.0%), pyrexia and anemia (6/14, 42.9%), asthenia (4/14, 28.6%), fatigue, diarrhea, headache, dizziness, dyspnoea, hypotension, decreased appetite, alanine aminotransferase (ALT), increased back pain, peripheral

oedema, and aspartate aminotransferase (AST) increased (3/14, 21.4%). All CRS events, assessed according to ASTCT 2019 criteria, were Grade 1 or 2. In this cohort, manifestations of CRS occurring in more than 1 subject included pyrexia (7/8, 87.5%), hypotension (5/8, 62.5%), hypoxia and tachycardia (3/8, 37.5%), and headache (2/8, 25.0%). Anemia and lymphopenia were the only Grade 3 or 4 events reported in more than 1 subject (2/14, 14.3%). A single subject (1/14, 7.1%) died of COVID infection in this cohort.

Efficacy in the NHL population as measured by overall response rate (objective response rate [ORR], complete response [CR] plus partial response [PR]) and was observed in nearly all cohorts, with responses seen more consistently in cohorts with a top dose of greater than 80 µg/kg. [Table 2](#) below presents the responses by cohort, as of 18 August 2021, for cohorts with a top dose of greater than or equal to 80 µg/kg in the efficacy evaluable population for NHL. The proposed plamotamab flat dosing regimen for the XmAb13676-03 study is represented below as “50 mg.”

Table 2: Overall Response Rate, Complete Response and Disease Control Rate for Overall Population and by Top Dose Level in Subjects with NHL from Study XmAb13676-01

Top Dose/Response	Efficacy Evaluable Population
Overall	
ORR	24/55 (43.6)
CR	11/55 (20.0)
DCR	32/55 (58.2)
80 µg/kg	
ORR	1/5 (20.0)
CR	0/5
DCR	2/5 (40.0)
125 µg/kg	
ORR	6/16 (37.5)
CR	5/16 (31.3)
DCR	10/16 (62.5)
170 µg/kg	
ORR	4/8 (50.0)
CR	2/8 (25.0)
DCR	5/8 (62.5)
250 µg/kg ^a	
ORR	6/12 (50.0)
CR	1/12(8.3)
DCR	5/12 (41.7)
360 µg/kg	
ORR	2/5 (40.0)
CR	1/5 (20.0)
DCR	4/5 (80.0)
50 mg	
ORR	5/9 (55.6)
CR	2/9 (22.2)
DCR	5/9 (55.6)

CR = complete response; DCR = disease control rate; ORR = objective response rate.

^a One subject received a single priming dose of 25 µg/kg and achieved a PR.

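### The plamotamab sentence in the synopsis and Section 7.1.1 starts every-2-week dosing one cycle too early and conflicts with the dosing tables, Table 9 and the dose rationale

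*Protocol*

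**What the plan says.** Section 7.1.1 describes weekly plamotamab for four doses in Cycle 1 and then states: "beginning with Cycle 2, plamotamab will be administered every 2 weeks". The sentence before it names the patients concerned as those in Part 1 and those randomized to Arm A in Part 2. The synopsis paragraph on dose administration says the same.

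Both places lead straight to a table. The synopsis adds "Refer to dosing table below". Section 7.1.1 continues "Subjects in Cohort 1A and Cohort 1B receive plamotamab according to the doses and schedule in" Table 12. In both tables one column is headed "Cycle 2 Days 1, 8, 15, and 22", and the last column opens every-2-week dosing at Cycle 3. Table 3 in Section 4.1.1 and Table 1 in SAP Section 3.1.1 are laid out in the same way.

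Section 2.4.2 describes the Phase 1 flat-dose cohort as "weekly titration of 0.8, 2, 20, 35 and 50 mg, followed by weekly dosing of 50 mg until Cycle 3", then every 2 weeks, and identifies that 50 mg regimen as the one proposed for this study. Section 2.4.3 gives the same pattern for the 20 mg regimen.

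For the randomized part, Section 7.1.1 says: "The dose and schedule of plamotamab for Part 2 will be determined in Part 1".

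**The concern.** The sentence and the table below it cannot both be followed in Cycle 2. This is the main dosing section for a CD3-engaging bispecific antibody, in a three-drug combination that Section 4.6 says had not yet been tested in humans. A site that followed the sentence would leave out two infusions, inside the period that the Part 1 safety evaluation must cover (at least through Cycle 4 Day 28).

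The dosing interval also drives another rule. Section 4.7 counts a held dose as missed after 7 days under weekly dosing and after 14 days under every-2-week dosing. Two consecutive missed doses can lead to discontinuation and require Medical Monitor approval to continue. If the Cycle 2 interval is unclear, so is the rule: a Cycle 2 dose held for 7 to 13 days is missed on one reading and not on the other.

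**Working it through.** **Step 1. Compare the sources.**

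| Source | Plamotamab in Cycle 2 | Every 2 weeks from |
|---|---|---|
| Synopsis, sentence | 2 infusions | Cycle 2 |
| Section 7.1.1, sentence | 2 infusions | Cycle 2 |
| Synopsis, dosing table | Days 1, 8, 15, 22 | Cycle 3 |
| Section 4.1.1, Table 3 | Days 1, 8, 15, 22 | Cycle 3 |
| Section 7.1.1, Table 12 | Days 1, 8, 15, 22 | Cycle 3 |
| SAP Section 3.1.1, Table 1 | Days 1, 8, 15, 22 | Cycle 3 |
| Section 5, Table 9, plamotamab row | Days 1, 8, 15, 22 marked | Cycle 3 (Days 1 and 15 marked) |
| Section 2.4.3, 20 mg regimen | weekly | Cycle 3 |
| Section 2.4.3, 50 mg regimen | weekly | Cycle 3 |

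The same column heading recurs in four tables, and both Table 9 and the narrative rationale agree with it. It is therefore not an artefact of reading the PDF. Figure 2, which is meant to show dose and schedule, is not reproduced in the text available and could not be checked.

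**Step 2. Count Cycle 2 under each reading.** The dosing tables list Cycle 2 Day 1 in two columns. It is counted once here, as in Table 9.

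- Infusions: 4 by the tables, 28/14 = 2 by the sentence. The sentence drops Days 8 and 22.
- Cohort 1A: 4 × 20 = 80 mg by the tables, 2 × 20 = 40 mg by the sentence.
- Cohort 1B: 4 × 50 = 200 mg by the tables, 2 × 50 = 100 mg by the sentence.

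**Step 3. Carry it forward, only on the supposition that the sentence was followed.** Cycle 1 is the same on both readings: 0.8 + 2 + 20 + 20 = 42.8 mg in 1A and 0.8 + 2 + 20 + 35 = 57.8 mg in 1B. Cycles 3 and 4 are also the same: 4 × 20 = 80 mg and 4 × 50 = 200 mg.

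- Through Cycle 2, 1A: 42.8 + 40 = 82.8 against 42.8 + 80 = 122.8 mg; 40/122.8 = 32.6% less.
- Through Cycle 2, 1B: 57.8 + 100 = 157.8 against 57.8 + 200 = 257.8 mg; 100/257.8 = 38.8% less.
- Through Cycle 4 Day 28, 1A: 162.8 against 202.8 mg; 40/202.8 = 19.7% less.
- Through Cycle 4 Day 28, 1B: 357.8 against 457.8 mg; 100/457.8 = 21.8% less.
- Infusions through Cycle 4: 4 + 2 + 2 + 2 = 10 against 4 + 4 + 2 + 2 = 12.

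No sample size, power or alpha figure depends on any of this.

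**The case against.** The best reply is that the protocol resolves the conflict itself. In Section 7.1.1 a cohort-specific instruction follows the general sentence at once and sends Cohorts 1A and 1B to Table 12 for schedule as well as dose. The synopsis points to its table in the same way. Sections 5 and 7.6.1 assign timing to Table 9, which marks plamotamab on Cycle 2 Days 8 and 22. Patients attend on those days in any case, because Section 7.1.2 and Table 14 give tafasitamab weekly through Cycle 3. To omit the plamotamab infusion, a site would have to overlook two tables during a visit that was already taking place. All of this stands, and it is why the severity is low. It does not make the sentence correct.

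A reader might take Table 10 as support for the sentence, since its Cycle 2 columns show only Days 1 and 15. But Table 10 schedules samples and ECGs, not infusions, and sampling can be sparser than dosing. It does not outweigh the explicit administration row in Table 9.

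In the other direction, the note to Table 2 counts 8 doses over the first two cycles, which fits weekly dosing. That is an evaluability rule from the Phase 1 study, so it is only indirect support and the conclusion does not need it.

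**Conclusion.** The sentence is wrong as written in both places. Weekly dosing in Cycle 2 is the evident intent, and every dosing table and the rationale state it. This is a low-severity internal inconsistency in an operative instruction; the schedule itself is not in question. Its size is 2 infusions instead of 4 in Cycle 2 (40 instead of 80 mg in 1A, 100 instead of 200 mg in 1B), together with an ambiguous missed-dose rule in that cycle.

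A reader might infer more in three ways, and the documents support none of them.

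- **That patients were or would be underdosed by 20% to 39%.** The cumulative percentages hold only if a site preferred the sentence to the tables, which is unlikely. SAP Section 1 reports that the study ended with 3 subjects, and Cohort 1B was to open only after 1A had completed enrollment, so the 1B figures describe the plan.
- **That the sentence creates a measurable risk of cytokine release syndrome.** Section 11.8 notes a possible link with longer dosing intervals, but nothing quantifies it for a 14-day gap in Cycle 2.
- **That the error settles, or leaves untouched, the Part 2 regimen.** The sentence does cover Part 2 Arm A by name. However, that schedule was still to be chosen from Part 1, and Section 4.1.2 requires a protocol revision before Part 2 begins.

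The conclusion assumes that Figure 2 does not contradict the tables.

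**What to change.** Replace the sentence in the synopsis and in Section 7.1.1 with wording to this effect: *In Cycles 1 and 2, give plamotamab once every 7 days (± 1 day), four doses per cycle, on Days 1, 8, 15 and 22. From Cycle 3 onward, give it every 2 weeks.* Keep the ± 1 day window, which the present Cycle 1 wording carries. State that this applies to Part 1 Cohorts 1A and 1B, and that the Part 2 Arm A schedule will be set from Part 1 through the planned protocol revision. Check Figure 2 against the corrected text.

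Optional tidying in the same edit: add 35 mg and 50 mg to the synopsis list of anticipated doses, which stops at 20 mg although its own table goes to 50 mg. Also drop Day 1 from the second Cycle 2 column of the dosing tables, since it already has its own column.

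The cost is one sentence corrected in two places, with no extra patients, visits or analyses. With the study terminated, the practical use is to have the planned regimen described correctly in the study report and in any later reuse of this text.

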7.1.2. Tafasitamab Dosing Scheme and Premedications

All subjects will receive tafasitamab. Priming doses will be administered on Days -8 and -4 of a 1-week run-in period. During the first 3 cycles of the study, tafasitamab will be infused on Day 1, Day 8, Day 15, and Day 22 of each cycle. Thereafter, tafasitamab will be administered on a biweekly (every 14 days) basis, with infusions on Days 1 and 15 of each 28-day cycle until disease progression, unacceptable toxicity, or discontinuation for any other reason, whichever comes first

(Table 14). The first infusion of tafasitamab is given at a rate of 70 mL/h for the first 30 minutes; then, the rate is increased so that the infusion is administered within 1.5 to 2.5 hours. All subsequent infusions should be infused 1.5 to 2 hours. Administer prior to plamotamab on days when both products are given.

Table 14: Tafasitamab Dosing Scheme

Day -8 and -4 (Priming Dose)	Cycle 1 Days 1, 8, 15, 22	Cycle 2 Days 1, 8, 15, 22	Cycle 3 Days 1, 8, 15, 22	Cycle 4 and Subsequent Q2W Dosing
12 mg/kg	12 mg/kg	12 mg/kg	12 mg/kg	12 mg/kg

Q2W = every 2 weeks.

Tafasitamab should be administered according to the package insert (Monjuvi[®] PI, 2021) and by a healthcare professional with immediate access to emergency equipment and appropriate medical support to manage infusion-related reactions.

All subjects will be premedicated for tafasitamab doses as indicated in Table 15.

Table 15: Premedications for Tafasitamab

	Day -8 and Day -4	Cycle 1 Day 1	Cycle 1 Days 8, 15, and 22	Subsequent Cycles
Dexamethasone (on days when both tafasitamab and plamotamab are administered)	Not applicable	20 mg IV approximately 30 to 60 minutes prior to the start of tafasitamab	20 mg IV approximately 30 to 60 minutes prior to the start of tafasitamab	Required prior to the start of tafasitamab if infusion-related reaction observed Optional if no reaction
Prednisone or equivalent (if tafasitamab alone is administered)	100 mg IV 30 – 60 minute prior to the start of the infusion	-	100 mg IV 30 – 60 minute prior to the start of the infusion	Required if infusion-related reaction observed Optional if no reaction
Diphenhydramine	50 – 100 mg PO or IV approximately 30 – 60 minutes prior	50 – 100 mg PO or IV approximately 30 – 60 minutes prior	Required if infusion-related reaction observed Optional if no reaction	Required if infusion-related reaction observed Optional if no reaction
Acetaminophen	650 – 1000 mg PO approximately 30 – 60 minutes prior	650 – 1000 mg PO approximately 30 – 60 minutes prior	Required if infusion-related reaction observed Optional if no reaction	Required if infusion-related reaction observed Optional if no reaction

IV = intravenous; PO = by mouth.

On study days when both tafasitamab and plamotamab are administered, administer a single dose of dexamethasone in Cycle 1 prior to the start of the tafasitamab infusion. If plamotamab is held and tafasitamab alone is administered, premedication with prednisone or equivalent is required with the first 3 doses only and subsequently required if infusion-related reaction is observed.

For subjects not experiencing infusion-related reactions during the first 3 infusions, premedication is optional for subsequent infusions. If a subject experiences an infusion-related reaction, administer premedications before each subsequent infusion.

In the event of the discontinuation of tafasitamab, in the absence of disease progression, and if the subject is still receiving benefit from the study treatment, subjects may continue with the other study treatment(s).

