7.10. Study Drug Administration

7.10.1. Plamotamab

Plamotamab has previously been given to humans in a Phase 1 clinical study (XmAb13676-01). In the XmAb13676-01 study, CRS was frequently observed, especially with the Cycle 1 Day 1 dose (Section 2.4). Either a Principal Investigator or Sub-Investigator (MD) must be readily available during and for a minimum of 24 hours after administration of a plamotamab dose.

All subjects will be premedicated in Cycle 1 with dexamethasone 20 mg IV approximately 30 to 60 minutes prior to the start of the tafasitamab infusion. During Cycle 1, if tafasitamab infusion is held for any reason, dexamethasone will be given 1 hour prior to the start of the plamotamab administration. After Cycle 1, premedication with dexamethasone is not required and is permitted at the Investigator's discretion. (Cetirizine or other antihistamine may be used in place of diphenhydramine).

Plamotamab administration should begin as soon as possible after the dosing solution is prepared. If there is a delay in administration, it may be stored at [REDACTED].

Plamotamab SHOULD NOT BE ADMINISTERED AS AN IV PUSH OR BOLUS.

Study drug will be administered as an open-label solution at a [REDACTED] using a dedicated infusion set. Precautions for CRS or infusion reactions/anaphylaxis should be observed during plamotamab administration. Due to the possibility that CRS or allergic/infusion reactions may occur, emergency resuscitation equipment (a “crash cart”) and medications including steroids and tocilizumab should be present in the immediate area where subjects are receiving their infusions. Additional supportive measures should be available and may include, but are not limited to, acetaminophen, antihistamines, corticosteroids, IV fluids, bronchodilators, epinephrine, vasopressors, and oxygen.

Management of CRS and other infusion-related reactions will be per standard investigational site procedures, or alternatively, as outlined in this protocol. Please refer to [Section 4.6](#) for management of infusion reactions/CRS and neurotoxicity, if needed.

Vital signs will be measured and recorded as described in [Section 7.6.1](#).

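### Cycle 1 steroid premedication instructions contradict each other: plainly when tafasitamab is given alone, and through one unscoped sentence when both antibodies are given

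*Protocol*

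**What the plan says.** The instructions are spread over Protocol Sections 7.1.1, 7.1.2 and 7.10.1.

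- **Section 7.1.2, schedule.** All subjects start with a tafasitamab run-in: "Priming doses will be administered on Days -8 and -4 of a 1-week run-in period". In the first three cycles "tafasitamab will be infused on Day 1, Day 8, Day 15, and Day 22 of each cycle".
- **Section 7.1.2, Table 15, dexamethasone row** (days with both antibodies). 20 mg IV on C1D1 and on C1D8, C1D15 and C1D22, with no condition. It depends on a previous reaction only in later cycles.
- **Section 7.1.2, Table 15, prednisone row**, labelled "Prednisone or equivalent (if tafasitamab alone is administered". 100 mg IV on Days -8 and -4, a dash on C1D1, and 100 mg IV with no condition on C1D8, C1D15 and C1D22.
- **Section 7.1.2, Table 15, diphenhydramine and acetaminophen rows.** Given on Days -8, -4 and C1D1. From C1D8 they depend on whether a reaction has occurred.
- **Section 7.1.2, text after Table 15.** On days with both antibodies, sites are to "administer a single dose of dexamethasone in Cycle 1 prior to the start of the tafasitamab infusion". When plamotamab is held, "premedication with prednisone or equivalent is required with the first 3 doses only and subsequently required if infusion-related reaction is observed". A general sentence follows: "For subjects not experiencing infusion-related reactions during the first 3 infusions, premedication is optional for subsequent infusions".
- **Section 7.1.1, Table 13.** The steroid row is labelled "Dexamethasone (if plamotamab alone is administered": 20 mg in Cycle 1, optional later.
- **Section 7.10.1**, under the Plamotamab heading. "All subjects will be premedicated in Cycle 1 with dexamethasone 20 mg IV approximately 30 to 60 minutes prior" to tafasitamab. After Cycle 1, dexamethasone is at the investigator's discretion.

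**The concern.** The run-in doses take two of the three infusions in the count and C1D1 takes the third, so the relaxation arrives at C1D8. By Table 12, plamotamab is still being stepped up then: C1D8 and C1D15 are dose increases in both cohorts, and C1D22 is a further increase in Cohort 1B. In Section 2.4, Phase 1 CRS was reported at flat doses of 0.8, 2, 20 and 35 mg, which are the Cycle 1 doses here.

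CRS incidence is part of the Part 1 primary endpoint (Section 4.2.1), and the run-in safety evaluation feeds the choice of dose level (Section 4.1.1). If sites act on different instructions, infusion-reaction rates could reflect local premedication practice as well as the regimen. CRS rates could too, if sites take the general sentence to cover dexamethasone.

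**Working it through.** No power, alpha or sample-size figure is involved, so there is no plan figure to reproduce. The check counts infusions from the Section 7.1.2 schedule and sets the instructions side by side.

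**Step 1: count.** Two run-in infusions plus four in Cycle 1 give six: Day -8 = 1, Day -4 = 2, C1D1 = 3, C1D8 = 4, C1D15 = 5, C1D22 = 6. A rule that relaxes after three infusions starts at C1D8.

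**Step 2: tafasitamab alone, no reaction so far, run-in counted.**

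| Infusion | Day | Table 15, prednisone | Text after Table 15 | Agree |
|---|---|---|---|---|
| 1 | Day -8 | 100 mg | required | yes |
| 2 | Day -4 | 100 mg | required | yes |
| 3 | C1D1 | dash | required | no |
| 4 | C1D8 | 100 mg, no condition | optional | no |
| 5 | C1D15 | 100 mg, no condition | optional | no |
| 6 | C1D22 | 100 mg, no condition | optional | no |

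All four Cycle 1 infusions differ. Through C1D22, Table 15 schedules 5 x 100 = 500 mg. The text requires 3 x 100 = 300 mg, if the 100 mg dose is assumed for C1D1 as well. The 300 mg is a floor, because optional doses may be added.

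**Step 3: sensitivity.**

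- *Reaction during infusions 1 to 3:* the text then also requires premedication on C1D8, C1D15 and C1D22. Only C1D1 still differs.
- *Count starting at C1D1 instead:* the text would require C1D1, C1D8 and C1D15 and leave C1D22 optional. C1D1 and C1D22 differ, 2 of 4.

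C1D1 conflicts in every case. The antihistamine and antipyretic rows of Table 15 switch at C1D8, which matches a three-infusion count only if the run-in is included, but the text does not say so.

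**Step 4: Arm B.** Arm B receives no plamotamab, so all its tafasitamab infusions are given alone. The text rule on prednisone is worded for plamotamab being held, which cannot literally happen in Arm B.

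- If the rule does reach Arm B, Step 2 applies.
- If it does not, Table 15 still conflicts with the general sentence on C1D8, C1D15 and C1D22 in a reaction-free subject.
- Either way, Table 15 gives Arm B no steroid on C1D1: the dexamethasone row is limited to days with both antibodies, and the prednisone row shows a dash.
- Section 7.10.1, taken literally, would give Arm B dexamethasone.

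**Step 5: both antibodies (Part 1 and Arm A).** Three instructions agree on Cycle 1 dexamethasone: Table 15, the paragraph before the general sentence in Section 7.1.2, and Section 7.10.1. Table 13 adds the same dose when plamotamab is given alone. Against them stands the general sentence. It names no drug, so read literally it makes dexamethasone optional on 3 of the 4 Cycle 1 plamotamab days for a reaction-free subject.

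**The case against.** The best defence concerns plamotamab recipients. Their Cycle 1 dexamethasone is specified several times and consistently, and specific instructions normally prevail over a general one. The general sentence can also be read as describing only the diphenhydramine and acetaminophen rows, which do become conditional at C1D8. The relaxation rule in Section 7.1.1, four consecutive infusions at a stable dose, cannot be met within Cycle 1. A reader might infer that CRS is measured under undefined steroid cover in both arms. The documents do not support that.

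Other parts of the defence also stand. On C1D8, C1D15 and C1D22 the conflict is required against optional, so a site that gives prednisone per Table 15 breaches neither instruction. Section 7.10.1 sits under the Plamotamab heading, so applying it to Arm B is strained. Section 4.6.1.2 states that CRS has not been seen in trials of tafasitamab plus lenalidomide. Section 7.2 requires medications to be recorded with date, time and dose, so actual cover can be described.

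Two things are not answered. No reading reconciles Table 15 with the text when tafasitamab is given alone. And the narrow reading of the general sentence needs to be written down: the sentence does not state it, and Table 13 lists the same two drugs for plamotamab in Cycle 1 and marks them required in later cycles.

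**Conclusion.** The point holds as a contradiction between operative premedication instructions.

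- **Tafasitamab alone:** Table 15 and the text differ on four of four Cycle 1 infusions for a reaction-free subject with the run-in counted, on two of four if the count starts at C1D1, and on C1D1 alone after a reaction during infusions 1 to 3. These figures for Arm B assume that the rule worded for held plamotamab extends to it, which the protocol leaves open.
- **Both antibodies:** one general sentence of unstated scope conflicts with otherwise consistent Cycle 1 dexamethasone instructions.
- **Section 7.10.1:** its reference to all subjects is not expressly limited to plamotamab recipients.

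The likely effect is variation between sites in steroid cover, relevant mainly to infusion reactions. A reader might also infer that the CRS comparison between arms would be confounded. That does not follow: CRS is not expected with the Arm B regimen, and SAP Sections 1, 4.1 and 7 report early termination with 3 subjects and listings only, so no cohort or arm comparison will be made. The Part 2 primary endpoint is PFS by blinded independent review, and this point does not bear on how it is analysed.

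**What to change.** Reconcile Table 13, Table 15, the text after Table 15 and Section 7.10.1 into one premedication table with separate rows for days with both antibodies, days with tafasitamab alone (naming Arm B), and days with plamotamab alone. State:

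- whether the count of three includes Day -8 and Day -4;
- which drugs the optional rule covers;
- which subjects Section 7.10.1 addresses.

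The sponsor's clinical team decides which rule stands; this review takes no position on it.

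The cost is protocol wording. Section 4.1.2 already foresaw a protocol revision before Part 2, so the table matters now only if the protocol is resumed or reused. For the 3 enrolled subjects, list the steroid premedication actually given at each infusion beside the CRS and infusion-reaction listings. The data are already collected under Section 7.2, so this costs one additional listing.
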